15.3 Clinical Laboratory Evaluation

Listings and summary statistics at each assessment time will be presented using SI units. Normal ranges will be provided by the laboratory department, and out of range flags will be calculated based on the normal ranges. Laboratory data not transferred from the central laboratory in SI units will be converted to SI units before processing. Both original units and SI units will be provided in the SDTM domain.

Safety laboratory parameters are separated into:

- Hematology (including coagulation)
- Biochemistry
- Urinalysis
- Other tests

Hematology, biochemistry, and coagulation will be summarized by treatment and time point using descriptive statistics for baseline (see definition in Section 9), each evaluation during the study, and change from baseline to each evaluation.

Listings of abnormal test results (low and high) will also be provided.

15.4 Vital Signs

Vital signs data will be summarized by treatment and time point using descriptive statistics for baseline (see definition in Section 9), each evaluation during the study, and change from baseline to each evaluation. Listings of vital sign data will be provided.

Vital sign summaries will include all vital sign assessments from the on-treatment period. All vital sign assessments will be listed, and those collected outside the on-treatment period will be flagged in the listing.

15.5 Other Safety or Tolerability Evaluations

Safety ECG data will be summarized by treatment and by time point using descriptive statistics for baseline (see definition in Section 9), each evaluation during the study, and change from baseline to each evaluation. A listing of safety ECG data will be provided.

ECG summaries will include all ECG assessments from the on-treatment period. All ECG assessments will be listed.

The analysis of QT data is complicated by the fact that the QT interval is highly correlated with heart rate. Because of this correlation, formulas are routinely used to obtain a corrected value, denoted QTc, which is independent of heart rate. This QTc interval is intended to represent the QT interval at a standardized heart rate. The QT interval will be corrected for heart rate by the Fridericia's formula, QTcF, defined as

$$QTcF = \frac{QT}{\sqrt[3]{RR}} ,$$

where RR represents the RR interval of the ECG in seconds and can be estimated as 60/Heart Rate.

Investigator-reported interpretation results will also be tabulated by study intervention and time point using the number and percentage of participants for each interpretation category (Normal, Abnormal Not Clinically Significant [NCS], Abnormal Clinically Significant [CS]). Abnormality reason will also be displayed.

16 Analyses of Other Endpoints/Estimands

16.1 Pharmacokinetics

PK evaluation will be performed by Nuvisan GmbH.

All statistical analyses and descriptive summaries of PK data will be performed on the PK Analysis Set.

16.1.1 Descriptive Statistics of PK Concentration Data

PK measurements of EE, NET, as well as **CCI** will be descriptively summarized using: number of non-missing observations (n), arithmetic mean (Mean), SD, coefficient of variation (CV%), minimum (Min), median (Median) and maximum (Max).

Descriptive statistics will only be calculated for $n > 2$ in which a measurement of BLQ represents a valid measurement and will be taken as zero for summary statistics of PK concentration data.

Any mean or median value that is below the lower limit of quantification will be shown as BLQ.

Descriptive statistics of PK concentration data will be calculated using values with the same precision as the source data and rounded for reporting purposes only. In export datasets, as well as in the SDTM PC domain, PK concentrations will be provided with full precision and will not be rounded.

The following conventions will be applied when reporting descriptive statistics of PK concentration data:

N	0 decimal place
Mean, Min, Median, Max:	3 significant digits
SD:	4 significant digits
CV%:	1 decimal place

16.1.2 Descriptive Statistics of PK Parameter Data

PK parameter data of EE and NET on Day 1 and Day 15 as well as **CCI** on Day 4 and Day 15 will be summarized using: number of non-missing observations (n), arithmetic mean (Mean), SD, coefficient of variation (CV%), minimum (Min), median (Median), maximum (Max), geometric mean (GeoMean), the geometric coefficient of variation (GeoCV) and the 95% confidence interval for the GeoMean (LCI 95% GM, UCI 95% GM). For PK parameters related to time (e.g. t_{max} , t_{lag} , t_{last}), only n, Min, Median, and Max may be reported.

Descriptive statistics will only be calculated for a PK parameter when $n > 2$.

PK parameters read directly from the measurements (i.e., C_{max}) will be reported with the same precision as the source data. All other PK parameters will be reported to 3 significant figures. In export datasets, as well as in the SDTM PP domain, PK parameters will be provided with full precision and will not be rounded. Descriptive statistics of PK parameter data will be calculated using full precision values and rounded for reporting purposes only.

The following conventions will be applied when reporting descriptive statistics of PK parameter data:

N	0 decimal place
Mean, Min, Median, Max, GeoMean, 95% CI:	3 significant digits
SD:	4 significant digits
CV%, GeoCV%:	1 decimal place

16.1.3 Statistical Analysis of PK Parameter Data

Analysis of Primary Endpoints

A general linear model with a fixed effect for TREATMENT and a random effect for SUBJECT will be applied to log-transformed PK parameters C_{max} and $AUC_{0-\infty}$ based on the PK analysis set to assess the effect of multiple doses of evobrutinib on EE/NET PK. Treatment differences on the log scale of EE/NET with evobrutinib vs EE/NET alone (Day 15 vs Day 1) will be estimated for C_{max} and $AUC_{0-\infty}$ together with their 90% CIs.

Point estimates and CIs will be back transformed to the original scale.

Analysis of Secondary Endpoints

The same analysis model as described for the primary endpoints will be provided for the secondary endpoint $AUC_{0-t_{last}}$ of EE/NET.

16.1.4 General Specifications for PK Concentration and PK Parameter Data

Predose samples that occur before the first drug administration will be assigned a time of 0 hours, as if the sample had been taken simultaneously with the study intervention administration. Same applies to the predose sample after multiple doses.

Predose or trough samples which have been taken after the subsequent dosing will be reported as a protocol deviation. The resulting concentrations will be included in concentration listings but excluded from descriptive statistics of concentrations and from PK parameter estimation.

Values BLQ will be taken as zero for summary statistics of PK concentration data, PK parameter estimation (e.g., AUC) and for graphical presentations.

Missing concentrations (e.g., no sample, insufficient sample volume for analysis, no result or result not valid) will be reported generally as “N.R.”. A participant who withdraws prior to the last planned observation will be included in the analyses up to the time of discontinuation if still included in the PK analysis set.

If samples are collected outside of 10% of the PK sampling time windows defined in the CSP in Section 8.4, these will be included in the PK parameter estimation (NCA) but will be excluded from the concentration summary and mean/median concentration plots.

PK concentrations which are erroneous due to a sampling processing or analytical error (as documented in the bioanalytical report) may be excluded from the PK analysis if agreed by the Sponsor. In this case the rationale for exclusion will be provided in the CSR. Any other PK concentrations that appear implausible to the Clinical Pharmacologist/Clinical PK/PD Scientist will not be excluded from the analysis. Any implausible data will be documented in the CSR.

If important protocol deviations occurred likely to affect the PK profile of participants as specified in Section 10.2.1, the impacted concentrations and PK parameters will be excluded from summary statistics and further statistical evaluation.

Any PK concentrations or PK parameters excluded from summary statistics will be included in participants listings and flagged; a reason for exclusion will be detailed in the CSR (e.g., a footnote or a table of exclusions). Any flags will be included in the study specific CDISC data sets.

PK concentrations and PK parameters excluded from summary statistics will not be included in mean/median figures. Mean plots will only contain values where $n > 2$.

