1.3 Schedule of Activities

Assessments & Procedures	Screening	Intervention Period (Days)																Safety Follow-up	Notes	
		-1	1	2	3	4	5	6	7	8	9	10	11	12	13	14	15	16	17	
Study Day	-28 to -2																		18	
Informed consent	X																			Prior to any Screening activity.
Eligibility criteria	X	X ^a																		a: For re-check of eligibility criteria on Day -1, see inclusion (Section 5.1) and exclusion criteria (Section 5.2).
Demography	X																			Demography to include, at minimum, age, sex, race, and ethnicity.
Medical history	X																			
Physical examination	X	X																X	Brief examination on Day -1 to check eligibility.	
Serum pregnancy test	X	X																X		
Viral serology, TSH and QuantiFERON® test	X																			
Clinical laboratory tests including FSH	X	X														X		X	Details in Appendix 5. FSH in postmenopausal women at Screening only.	
Drug screen, alcohol breath test, and SARS-CoV-2	X	X																		
24 hours Holter ECG	X																			At Screening: 24-hour Holter ECG of participants above 45 years of age (\pm 2 hours time window allowed).
12-lead ECG	X	X	X													X	X	X		On Days -1 and 14 (predose to COC administration on Days 1 and 15); on Days 1 and 15 at 2 hours postdose \pm 30 min; and on Day 18.

Assessments & Procedures	Screening	Intervention Period (Days)																Safety Follow-up	Notes	
		-1	1	2	3	4	5	6	7	8	9	10	11	12	13	14	15	16	17	
Study Day	-28 to -2																	18		
Vital signs	X	X	X			X										X			X	Includes height and weight (collection at Screening only). Predose and 4 and 6 hours postdose on Days 4 and 14.
CCl [REDACTED]																				
Participants resident in the CRU		<----->																		
COC oral administration			X														X		Single dose of EE/NET under fed conditions. For details on dosing see Section 6.1.	
PK samples COC			X	X	X	X											X	X	X	Days 1-4, 15-18: predose and 20 min, 40 min, 1, 1.5, 2, 3, 4, 6, 8, 12, 16, 24, 36, 48, 60 and 72 hours postdose (see Section 8.4).
Evobrutinib administration						X	X	X	X	X	X	X	X	X	X	X	X	X	Evobrutinib to be dosed in the morning and the evening approximately 12 hours apart for twice daily dosing under fed conditions (see Section 6.1).	
[REDACTED]																			CCl [REDACTED]	
AE		<----->																		
Concomitant medication review		<----->																		

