8.4 Pharmacokinetics

- The following PK parameters will be calculated, when appropriate: PK parameters will be calculated for all analytes and unless otherwise noted.

Symbol	Definition
$AUC_{0-\infty}$	The AUC from time zero (= dosing time) up to infinity with extrapolation of the terminal phase.
$AUC_{0-t_{last}}$	The AUC from time zero (= dosing time) to the time of the last quantifiable concentration (t_{last}).
C_{max}	Maximum observed concentration.
t_{max}	The time to reach the C_{max} in a dosing interval.
$t_{1/2}$	The terminal half-life.
CL/F	The apparent total body clearance following extravascular administration (EE, NET, CCI [REDACTED] only).
V_z/F	The apparent volume of distribution during the terminal phase following extravascular administration (EE, NET, CCI [REDACTED] only).
CCI [REDACTED]	[REDACTED]
[REDACTED]	[REDACTED]

- Whole blood samples of approximately 4 mL for measurement of plasma concentrations of EE/NET and 3 mL for measurement of **CCI** [REDACTED] and **CCI** [REDACTED] will be collected. Collection times are specified in the Schedule of Assessments (see Section 1.3).
- EE/NET samples will be collected starting on Day 1 and Day 15 with timepoints predose through 72 hours postdose. On Day 4, the 72 hours postdose sample will be collected prior to evobrutinib dosing.

CCI [REDACTED]

- The actual date and time (24-hour clock time) of each sample will be recorded to calculate actual time elapsed since the prior dose administration.

- The quantification of EE/NET and evobrutinib in plasma will be performed using a validated assay method. CCI [REDACTED]
- Remaining samples collected for analyses of EE/NET and CCI [REDACTED] concentrations may also be used to evaluate safety or efficacy aspects related to concerns arising during or after the study. Additionally, remaining plasma samples may be used for investigation of other CCI [REDACTED].
- Details on processes for collection and handling of these samples are in the Laboratory Manual. Retention time and possible analyses of samples after the end of study are specified in the respective ICF.

The accepted time deviations from planned PK sampling times that will not be considered a protocol violation are listed below. Any deviation from these time windows requires a comment in the eCRF and may be discussed in the data review meeting.

Procedure	Time Point (Relative Time)	Window Allowance
Pharmacokinetics	Predose	Day 1: - 60 min Day 4: - 60 min Day 15: - 5 min

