	0.25 to 1 hours postdose	± 2 min
	> 1 to 12 hours postdose	± 5 min
	> 12 to 24 hours postdose	± 15 min
	> 24 to 72 hours postdose	± 30 min

CCI

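### Does the SAP's 10% sampling-time rule wrongly remove accepted samples from the concentration summaries?

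*SAP*

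**What the plan says.** SAP 16.1.4 (General Specifications for PK Concentration and PK Parameter Data) opens its rule on off-time samples with "If samples are collected outside of 10% of the PK sampling time windows defined in the CSP in Section 8.4". These samples enter the PK parameter estimation but "will be excluded from the concentration summary and mean/median concentration plots". The same section deals with predose samples: "Predose samples that occur before the first drug administration will be assigned a time of 0 hours".

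Protocol 8.4 introduces its window table with "The accepted time deviations from planned PK sampling times that will not be considered a protocol violation are listed below". The allowances are ±2 min for the band "0.25 to 1 hours postdose", ±5 min up to 12 h, ±15 min up to 24 h and ±30 min up to 72 h. The predose allowances are 60 min before dosing on Days 1 and 4, and 5 min on Day 15. For samples beyond these limits: "Any deviation from these time windows requires a comment in the eCRF".

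The EE/NET schedule in protocol 1.3 is "predose and 20 min, 40 min, 1, 1.5, 2, 3, 4, 6, 8, 12, 16, 24, 36, 48, 60 and 72 hours postdose". SAP 16.1.1 applies the concentration summaries to "PK measurements of EE, NET, as well as" a redacted analyte. SAP 16.1.5.1 bases PK parameters on actual elapsed time. SAP 16.1.6.1 lists a percentage time deviation for each sample but gives no denominator and no threshold.

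**The concern.** The only base that the sentence names for its 10% is the set of windows in protocol 8.4. A tenth of a window is narrower than the window. Taken at its word, the SAP would therefore remove samples that were drawn within the protocol's accepted limits. It does not say whether the 10% is a share of the window, a margin beyond it, or a share of something else such as nominal time.

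If the narrow reading were programmed, the nominal-time concentration tables and the mean and median plots could lose many properly timed samples, and each loss would need a flag and a stated reason in the CSR. Two programmers could also produce different tables from the same text.

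**Working it through.** **Inputs.** The 16 postdose EE/NET times come from protocol 1.3 and the windows from protocol 8.4. By band, the times are 20, 40 and 60 min (3 times); 1.5, 2, 3, 4, 6, 8 and 12 h (7); 16 and 24 h (2); and 36, 48, 60 and 72 h (4). 3 + 7 + 2 + 4 = 16. The plan gives no figure of its own to reproduce.

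**Limits under each reading, in minutes either side of nominal.** With *w* the ± allowance and *t* the nominal time:

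| Band | Times | *w* | 0.10 × *w* | 0.10 × 2*w* | 1.10 × *w* | 0.10 × *t* |
|---|---|---|---|---|---|---|
| 20 min to 1 h | 3 | 2 | 0.2 | 0.4 | 2.2 | 2 to 6 |
| >1 to 12 h | 7 | 5 | 0.5 | 1 | 5.5 | 9 to 72 |
| >12 to 24 h | 2 | 15 | 1.5 | 3 | 16.5 | 96 to 144 |
| >24 to 72 h | 4 | 30 | 3 | 6 | 33 | 216 to 432 |

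**Narrow readings.** Under 0.10 × *w* the limit is 12 seconds in the first band and 30 seconds in the second, which together hold 3 + 7 = 10 of the 16 times. Assume that times are recorded to the whole minute:

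- A sample 1 min off nominal is dropped at 3 + 7 = 10 of 16 times.
- A sample 2 min off is dropped at 3 + 7 + 2 = 12 of 16.
- A sample 4 min off is in window at 7 + 2 + 4 = 13 times and is dropped at all 13.

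The column 0.10 × 2*w* applies a tenth of the full width on each side. It gives 3 of 16, 10 of 16 and 9 of 13 at the same offsets. This is a strained construction: a band one tenth as wide as the window and centred on nominal is simply 0.10 × *w*.

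These figures count sampling times at hypothetical offsets. They do not count samples lost, which depends on punctuality that the documents do not give.

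**Wider readings.** 1.10 × *w* exceeds *w* in every band, so no accepted postdose sample is dropped. For 10% of nominal time, compare *w*/*t* with 10%. The ratio runs from 5/720 = 0.69% at 12 h (and 30/4320 = 0.69% at 72 h) up to 2/20 = 10.0% at 20 min. At 20 min the limit equals the window, and elsewhere it is wider. Again no accepted EE/NET postdose sample is dropped.

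One reservation applies. The window table starts at 0.25 h. If the redacted analyte is sampled at 15 min, which cannot be seen, then 2/15 = 13.3% and 10% of nominal would be narrower than the window at that time.

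**Predose.** 10% of the allowance would be 6 min (Days 1 and 4) or 0.5 min (Day 15). 10% beyond it would be 66 or 5.5 min. The SAP sets predose samples to 0 h, so a percentage of nominal time has no practical meaning there.

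**What depends on the rule.** Only the concentration summary and the mean and median plots. The primary and secondary PK endpoints are NCA parameters, computed from actual times with these samples included. The listings in SAP 16.1.6.1 and the individual actual-time plots in SAP 16.1.6.2 keep the data.

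**The case for a change.** The best case for a change is that an analysis plan should state the rule that is to be programmed, and this one does not. Depending on the reading, the limit at 72 h is ±3, ±33 or ±432 min, a 144-fold spread (432/3). The narrow reading bites hardest at early times, where the windows are smallest and where NET peaks (1 to 3 h, protocol 2.2). With at most 20 participants, and summaries calculated only for n > 2, early points could become thin or vanish.

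The ambiguity stands: neither document settles the base of the 10%, and the listing column for percentage deviation does not help. The predicted harm is weaker. It needs someone to program a limit of seconds against a protocol that allows minutes. It then needs nobody to notice, although the tables show n, SAP 16.1.4 requires each exclusion to be flagged and explained, and PK-relevant deviations go to a data review meeting before database lock (SAP 10.2.1).

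The obvious rewrites also have costs. Excluding everything outside the protocol window would delete the SAP's tolerance rather than clarify it. Forbidding nominal time as the base would rest on a 15-min sample that nobody can see in the documents. Exempting predose samples would keep in the summaries a Day 15 predose sample taken, say, 40 min early, although its window is 5 min.

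**Conclusion.** No change to the plan follows. The sentence is loosely worded and leaves out what the 10% refers to, but this is missing detail that a PK analyst would fill sensibly. Both workable meanings keep every EE/NET postdose sample that protocol 8.4 accepts. The reading that does harm implies a limit of 12 or 30 seconds at 10 of 16 times, and its effects would be visible before reporting.

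Even on that reading the effect on Cmax, AUC and the 90% CIs is nil, because the NCA retains the samples at actual times. Only descriptive tables and nominal-time plots could differ, and the listings would let a reader rebuild them.

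This rests on the visible EE/NET schedule. The redacted analyte's times cannot be checked. The offset counts assume whole-minute recording.

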16.1.5 Estimation of Pharmacokinetic Parameters

The computer program Phoenix® WinNonlin® version 6.4, or higher (Certara, L.P., [name]) will be used to derive PK parameters applying NCA.

The statistical software SAS® (Statistical Analysis System, SAS-Institute, Cary NC, USA, windows version 9.1 or higher) will be used to generate additional PK parameters and produce tables, listings, and figures.

16.1.5.1 Estimation of Pharmacokinetic Parameters in Plasma

PK parameters will be calculated using the actual elapsed time since dosing. If the actual sampling time is missing, calculations may be performed using the scheduled time. Details (e.g., number of

samples, participants affected) will be described in the CSR. If actual dosing time is missing, scheduled time might be used for NCA after performance of adequate plausibility checks and agreement with the sponsor. Decision and rational should be included in the CSR. Otherwise, there will be no further imputation of missing data.

The following PK parameters will be calculated, when appropriate: PK parameters will be calculated for all analytes and unless otherwise noted.

Symbol	Definition
AUC _{0-∞}	The AUC from time zero (= dosing time) up to infinity with extrapolation of the terminal phase.
AUC _{0-t_{last}}	The AUC from time zero (= dosing time) to the time of the last quantifiable concentration (t _{last}).
C _{max}	Maximum observed concentration.
t _{max}	The time to reach the C _{max} in a dosing interval.
t _{1/2}	The terminal half-life.
CL/F	The apparent total body clearance following extravascular administration (EE, NET, CCI [REDACTED] only).
V _z /F	The apparent volume of distribution during the terminal phase following extravascular administration (EE, NET, CCI [REDACTED] only).
[REDACTED]	CCI [REDACTED] [REDACTED] [REDACTED]
[REDACTED]	[REDACTED] [REDACTED]

Additional PK parameters may be calculated where appropriate.

Units for PK parameter outputs will be based on concentration and dose units used in the study, unless otherwise specified. If concentration data units change within the study, PK parameters will be reported using consistent units throughout study outputs. In such cases, the Sponsor will specify relevant units for reporting before the final PK evaluation.

The parameters C_{max} and t_{max} will be obtained directly from the concentration-time profiles. If C_{max} occurs at more than one timepoint, t_{max} will be assigned to the first occurrence of C_{max}.

The following PK parameters will be calculated for diagnostic purposes and listed, but will not be summarized:

- First (λ_z low) and last (λ_z up) time point of the time interval of the log-linear regression to determine λ_z .
- Number of data points (N λ) included in the log-linear regression analysis to determine λ_z .
- Goodness of fit statistic (adjusted Rsq) for calculation of λ_z .
- AUC from time t_{last} extrapolated to infinity given as percentage of AUC_{0-∞}. (AUC_{extra%})

- Span ratio of interval over which $t_{1/2}$ was estimated/ $t_{1/2}$

The regression analysis should contain data from at least 3 different time points in the terminal phase consistent with the assessment of a straight line on the log-transformed scale. Phoenix WinNonlin “best fit” methodology will be used as standard. If warranted, further adjustment may be made by the pharmacokineticist, after agreement with the Sponsor. The last quantifiable concentration $>$ LLOQ should always be included in the regression analysis, while the concentration at t_{max} and any concentrations BLQ which occur after the last quantifiable data point $>$ LLOQ should not be used.

If $AUC_{extra\%} > 20\%$ and/or the coefficient of correlation (Rsq adj) of λ_z is < 0.8 and/or the observation period over which the regression line is estimated (span ratio) is less than 2-fold the resulting $t_{1/2}$, the rate constants and all derived parameters (e.g. $t_{1/2}$, $AUC_{0-\infty}$, CL/F, etc.) will be listed, flagged and included in the parameter outputs. Should more than 10% of subjects be flagged for AUC_{extra} and/or Rsq adj (for a particular analyte), a sensitivity analysis excluding flagged parameters may be performed after discussion with the Sponsor.

